- ^a Denotes a baseline assessment. Baseline is defined as before the first dose of study drug. Baseline assessments should be performed before administration of study drug. Subjects are enrolled following completion of eligibility requirements and who are randomized in the IWR. Subjects who are screened to determine eligibility, but do not undergo any baseline assessments are not considered enrolled. All eligible subjects must have documented COVID-19 infection diagnosed at the local level.
- ^b Study Day 1= first dose of study drug.
- ^c Assessments to be done daily.
- ^d X = clinic visit, ☎ = telephone visit. All post-baseline visits are ± 1 day in the event a visit occurs on a weekend.
- ^e Subjects will be given access and instructions to complete their eDiary on Day 1 using the web portal. Subjects will complete their eDiary daily from Day 1 through Day 15, Data to be collected in the eDiary daily will include 1) the number of study medication doses taken/missed and 2) the highest temperature recorded over the past 24 hour period.
- ^f All AEs must be recorded from the time of administration of the first dose of study drug until the subject has completed the end of study or early withdrawal. Any study procedure-related SAE that occurs after the study participant has signed the informed consent form and prior to administration of the first dose of study drug will be considered as Medical History. The study will collect only Treatment Emergent Adverse Events (TEAE).
- ^g Laboratory assessments including hematology (CBC including hemoglobin, hematocrit, WBC with differential, RBC, MCV, and platelet count) and clinical chemistry (albumin, ALT, ALP, AST, BUN, GGT, creatinine, electrolytes [sodium, potassium, carbon dioxide, chloride], glucose, total bilirubin, direct bilirubin, LDH, CRP) will be collected. Laboratory tests will be performed at the central laboratory.
- ^h Absence of fever is defined as ≤ 37.2°C oral.
- ⁱ The indicated assessments may be done at the investigators discretion but are not required.

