10.1 Study Visits

10.1.1 Screening/Baseline and Day 1 Visit

The following procedures and assessments will be done at the onsite Screening/Baseline and Day 1 visit:

- Verify subject has written notification from a local laboratory confirming COVID-19 infection within 72 hours of randomization (i.e., Day 1). In most instances, the Screening/Baseline visit will occur on the same date as Day 1. If needed, the Screening/Baseline may occur before Day 1 as long as randomization can be completed within the 72-hour window.
- Obtain informed consent
- Review of inclusion/exclusion criteria, including urine pregnancy test, if applicable
- Assign a subject ID number (ID number = XXX site number followed by 001, 002, 003 subject number)
- Obtain mid-turbinate nasal swab sample to be sent to the central laboratory to test for a baseline assessment and to test for viral shedding of COVID-19 by RT-PCR
- Draw blood for central laboratory testing
- Record demographics, medical history (including current COVID-19 symptoms), and concomitant medications
- Obtain vital signs (height, weight, heart rate, blood pressure, SpO2)
- Measure oral body temperature
- Perform randomization and dispensing of study drug
- Provide subject with instructions for accessing eDiary portal for collection of daily information
- Administer first dose of study drug after all assessments are completed
- Record of any TEAEs

10.1.2 Onsite Visits on Day 7, Day 15, Unscheduled Visit, Early Termination Visits / Telephone Visits on Day 21, Day 28

The following procedures and assessments will be done on Day 7, Day 15, Day 21, Day 28, and early termination by telephone or at onsite visits:

- Verify subject compliance for completing daily eDiary entries by accessing the web portal for the subject's eDiary
- Review concomitant medications and record any TEAEs
- Assess vital signs (heart rate, blood pressure, SpO2) during on-site visits only
- Measure oral body temperature
- Draw blood for central laboratory testing (Day 15, Unscheduled Visit and Early Termination) during on-site visits only

- Obtain mid-turbinate nasal swab sample for viral shedding test (Day 7, Day 15, and Early Termination Visits) for central laboratory during on-site visits only

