12.4 Adverse Events

12.4.1 Adverse Events

An AE is any symptom, physical sign, syndrome, or disease that either emerges during the study or, if present at screening, worsens during the study, regardless of the suspected cause of the event. All medical and psychiatric conditions (except those related to the indication under study) present at screening will be documented in the medical history eCRF. Changes in these conditions and new symptoms, physical signs, syndromes, or diseases should be noted on the AE eCRF during the rest of the study.

Subjects will be instructed to report AEs at each study visit. All AEs are to be followed up until resolution or a stable clinical endpoint is reached.

Each AE is to be documented on the eCRF with reference to date of onset, duration, frequency, severity, relationship to study drug, action taken with study drug, treatment of event, and outcome. Furthermore, each AE is to be classified as being serious or nonserious. Changes in AEs and resolution dates are to be documented on the eCRF.

For the purposes of this study, the period of observation for collection of AEs extends from the time the subject is administered study medication (Day 1) until Day 28 or early termination. Subjects with early termination will be followed up until Day 28. Follow-up of the AE, even after the date of therapy discontinuation, is required if the AE persists until the event resolves or stabilizes at a level acceptable to the investigator.

When changes in the intensity of an AE occur more frequently than once a day, the maximum intensity for the event should be noted. If the intensity category changes over a number of days, then those changes should be recorded separately (with distinct onset dates).

Specific guidelines for classifying AEs by intensity and relationship to study drug are given in [Table 3](#) and [Table 4](#).

Table 3. Classification of Adverse Events by Intensity

MILD: An event that is easily tolerated by the subject, causing minimal discomfort and not interfering with everyday activities.

MODERATE: An event that is sufficiently discomforting to interfere with normal everyday activities.

SEVERE: An event that prevents normal everyday activities.

Table 4. Classification of Adverse Events by Relationship to Study Drug

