12.4.3 Serious Adverse Event Reporting

An SAE occurring from the first dose administered until Day 28 must be reported to EVERSANA Pharmacovigilance and will be communicated to the Sponsor. Any such SAE due to any cause, whether or not related to the study drug, must be reported within 24 hours of occurrence or when the investigator becomes aware of the event. Notification can be made using the dedicated fax line or email for the EVERSANA Pharmacovigilance group:

EVERSANA Pharmacovigilance [contact]

EVERSANA Pharmacovigilance email address: [contact]

If the investigator contacts the EVERSANA Pharmacovigilance group by telephone, then a written report must follow within 24 hours and is to include a full description of the event and sequelae in the format detailed in the SAE reporting form.

EVERSANA Pharmacovigilance [contact]

The event must also be recorded on the standard AE eCRF. Preliminary reports of SAEs must be followed up by detailed descriptions later on, including clear and anonymized photocopies of hospital case reports, consultant reports, autopsy reports, and other documents when requested and applicable. SAE reports must be made whether or not the investigator considers the event to be related to the investigational drug.

Appropriate remedial measures should be taken to treat the SAE, and the response should be recorded. Clinical, laboratory, and diagnostic measures should be employed as needed in order to determine the etiology of the problem. The investigator must report all additional follow-up evaluations to the EVERSANA Pharmacovigilance group within 24 hours of becoming aware of the additional information or as soon as is practicable. All SAEs will be followed up until the investigator and Sponsor agree the event is satisfactorily resolved.

Any SAE that is not resolved by the end of the study or upon discontinuation of the subject's participation in the study is to be followed up until it either resolves, stabilizes, returns to baseline values (if a baseline value is available), or is shown to not be attributable to the study drug or procedures.

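### A serious event caused by a study procedure between consent and first dose is recorded only as medical history, with no explicit 24-hour reporting route and no place in any safety table

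*Protocol*

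**What the plan says.** Footnote f to the Schedule of Assessments (Protocol Section 10, Table 1) addresses this case directly. It covers "Any study procedure-related SAE that occurs after the study participant has signed the informed consent form" and directs that such an event "prior to administration of the first dose of study drug will be considered as Medical History". It then limits collection to treatment-emergent events.

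Other sections use the same start point:
- **Protocol 12.4.1:** "the period of observation for collection of AEs extends from the time the subject is administered study medication (Day 1) until Day 28" (early termination is the alternative end).
- **Protocol 12.4.3:** "An SAE occurring from the first dose administered until Day 28 must be reported to EVERSANA Pharmacovigilance". The 24-hour deadline that follows applies to SAEs in that window.
- **Protocol 12.1:** medical history covers conditions up to first dosing.

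On timing, Protocol 10.1.1 places screening and Day 1 on one date in most cases, but "the Screening/Baseline may occur before Day 1 as long as randomization can be completed within the 72-hour window". Within the visit, dosing comes after all assessments, including the swab and the blood draw.

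**The concern.** Footnote f already accepts that the event is serious, that it followed consent and that a study procedure caused it. It then files the event with the subject's background conditions. Among pre-dose events, this is the class for which the trial itself is responsible.

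If the rule is followed exactly, a site has no instruction to notify pharmacovigilance within 24 hours, and the study report has no table or listing in which the event would appear. At stake is the completeness of the record of serious harm from study procedures. The comparison of camostat with placebo is not at stake.

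**Working it through.** There is no figure in the plan to reproduce. The check sets the start points side by side and follows one event through them.

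**Start point of each rule**

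| Rule | Where | Starts at |
|---|---|---|
| Pre-dose procedures | Protocol 10.1.1 | After consent, before first dose |
| Medical history | Protocol 12.1 | Runs up to first dose |
| AE collection | Protocol 12.4.1 | First dose |
| SAE reporting, 24 hours | Protocol 12.4.3 | First dose |
| TEAE definition | SAP 4.3 and 4.3.1 | After first treatment |
| Safety Population | Protocol 13.2, SAP 2.5.4 | At least one dose taken |
| Endpoint: incidence of AEs and SAEs | Protocol 6.2.2, SAP 2.3.3 | Randomization |
| Event believed serious goes to expedited-reporting evaluation | Protocol 12.4.2 | No start date given |

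**Following one event.** Take a serious reaction to the baseline swab or blood draw, after consent and before dosing.

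1. *Recording.* Footnote f sends it to medical history, so it is on the eCRF but not as an AE or SAE.
2. *Reporting.* Section 12.4.3 does not cover it, and no other section gives it an explicit 24-hour route.
3. *Tables.* It precedes treatment, so it is not a TEAE. If it prevents dosing, the subject is also outside the Safety Population, to which the safety tables and the SAP 4.3.5 listings are confined. It could enter the AE data only if it worsened after the first dose.
4. *Efficacy.* If it follows randomization and leads to a hospitalization, ER visit or death recorded on the End of Study form, SAP 3.1 assumes it is COVID-related. It then counts as a primary-endpoint failure and still not as a harm.

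**Where the documents disagree**

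- *Endpoint window.* Protocol 10.1.1 lists randomization before the first dose. An SAE between the two lies inside the endpoint as defined but outside collection. The rule that the SAP prevails does not settle this, because both documents start the endpoint at randomization.
- *Seriousness rule.* The sentence in Section 12.4.2 has no time limit and requires sponsor evaluation; footnote f points the other way.
- *Procedure causality.* Section 12.4.3 follows an unresolved SAE until, among other outcomes, drug and procedures are ruled out as its cause. Procedure causality therefore matters to the protocol. The same reaction to the Day 7 swab would be in the reporting window.

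**Size of the exposure.** About 300 randomized subjects have the pre-dose swab and blood draw, as do any screen failures who reached those procedures. The gap is usually within one visit. The 72-hour limit runs from notification of the positive test to randomization, so it is a ceiling on the gap from consent to randomization and not its typical length. No document gives a rate of procedure-related SAEs, so no expected count can be derived.

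**The case against.** The strongest reply is that first dose is a deliberate and repeated start point, used in Sections 12.1, 12.4.1 and 12.4.3 and in the SAP's TEAE definition. This stands, and it limits what can be claimed.

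A reader might infer that footnote f contradicts Section 12.4.1, because that section's general definition covers a "disease that either emerges during the study or, if present at screening, worsens during the study". The same section then sets a specific collection window from first dose, which resolves the tension. The mismatches that remain are with the endpoint window and Section 12.4.2.

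A reader might also infer that the event is lost or removed from all oversight. It is not. It stays in the medical history, which Section 12.1 expressly extends past consent, and Section 12.4.2 could be read to bring it to the sponsor. What is missing is an explicit route.

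Three further replies have weight:
- The swab is repeated on Days 7 and 15 and the blood draw on Day 15, so harms from the same procedures are largely observable under the normal rules.
- A pre-dose event cannot be a SUSAR under Section 12.4.4, which requires a possible link to study treatment. Earlier notice would not lead to that form of report.
- The documents contain no stated requirement for 24-hour reporting before first dose. Whether the regulations they cite impose one cannot be judged here.

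None of these supplies the missing route or a place for the event in the safety report.

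**Conclusion.** The point holds, as a minor one. Followed literally, the plan records a procedure-related SAE between consent and first dose only as history, gives it no explicit 24-hour route and shows it in no safety table. The start point is consistent with Sections 12.1 and 12.4.1. It is inconsistent with an endpoint that begins at randomization and with the undated seriousness rule in Section 12.4.2.

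The number of events is likely to be small but cannot be estimated from the documents. That judgement rests on two facts: screening and Day 1 usually coincide, and the procedures are mainly a swab and a blood draw. A reader might infer that the rule distorts the safety comparison or the trial's conclusion. It does not: treatment-emergent tables are properly limited to post-dose events, and efficacy conclusions do not depend on this rule.

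**What to change.** 1. Amend footnote f and Section 12.4.3 so that a study-procedure-related SAE from signing of consent is recorded as an SAE, reported by the same 24-hour route and flagged as pre-treatment.
2. Add one listing to the SAP for these events, covering all consented subjects, including those never dosed. Leave the TEAE tables as they are.
3. Align Sections 12.1 and 12.4.1 to the same start point for this class of event. State in Protocol 6.2.2 and SAP 2.3.3 how the interval between randomization and first dose is handled.
4. Reconcile Section 12.4.2, which says that death and inpatient hospitalization are not SAEs in this study. Without this step, a procedure-related event that is serious on those grounds could still be excluded after steps 1 to 3.

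The cost is short edits to several protocol sections, a clarification in the SAP and one extra listing. Added site workload should be small.

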10.1 Study Visits

10.1.1 Screening/Baseline and Day 1 Visit

The following procedures and assessments will be done at the onsite Screening/Baseline and Day 1 visit:

- Verify subject has written notification from a local laboratory confirming COVID-19 infection within 72 hours of randomization (i.e., Day 1). In most instances, the Screening/Baseline visit will occur on the same date as Day 1. If needed, the Screening/Baseline may occur before Day 1 as long as randomization can be completed within the 72-hour window.
- Obtain informed consent
- Review of inclusion/exclusion criteria, including urine pregnancy test, if applicable
- Assign a subject ID number (ID number = XXX site number followed by 001, 002, 003 subject number)
- Obtain mid-turbinate nasal swab sample to be sent to the central laboratory to test for a baseline assessment and to test for viral shedding of COVID-19 by RT-PCR
- Draw blood for central laboratory testing
- Record demographics, medical history (including current COVID-19 symptoms), and concomitant medications
- Obtain vital signs (height, weight, heart rate, blood pressure, SpO2)
- Measure oral body temperature
- Perform randomization and dispensing of study drug
- Provide subject with instructions for accessing eDiary portal for collection of daily information
- Administer first dose of study drug after all assessments are completed
- Record of any TEAEs

10.1.2 Onsite Visits on Day 7, Day 15, Unscheduled Visit, Early Termination Visits / Telephone Visits on Day 21, Day 28

The following procedures and assessments will be done on Day 7, Day 15, Day 21, Day 28, and early termination by telephone or at onsite visits:

- Verify subject compliance for completing daily eDiary entries by accessing the web portal for the subject's eDiary
- Review concomitant medications and record any TEAEs
- Assess vital signs (heart rate, blood pressure, SpO2) during on-site visits only
- Measure oral body temperature
- Draw blood for central laboratory testing (Day 15, Unscheduled Visit and Early Termination) during on-site visits only

- Obtain mid-turbinate nasal swab sample for viral shedding test (Day 7, Day 15, and Early Termination Visits) for central laboratory during on-site visits only

10.1.3 Daily Assessments and Procedures by Subject

The following procedures and assessments will be done daily by the subjects themselves:

- Complete the daily eDiary entries using the web portal
- Measure oral body temperature
- Administer study drug QID

10.2 Informed Consent

Before performing any study-related procedures, the investigator (or designee) will obtain informed consent from the subject.

10.3 Study Procedures

Assessments and their timing are to be performed as outlined in the Schedule of Assessments (Table 1). Section 12.3 specifies laboratory assessment samples to be obtained.

Assessments and procedures scheduled at a visit where study drug is administered should be performed before administration of study drug unless otherwise indicated in the Schedule of Assessments (Table 1).

Efficacy assessments are described in Section 11 and include recording of hospitalization or death for any cause (if not hospitalized), resolution of fever, overall survival rate, and viral shedding.

Safety assessments are described in Section 12 and include concomitant medications, vital signs, laboratory assessments, pregnancy test, and AEs.

The investigator may, at his/her discretion, arrange for a subject to have an unscheduled assessment, especially in the case of AEs that require follow-up or are considered by the investigator to be possibly related to the use of study drug. The unscheduled visit page on the eCRF must be completed.

Study discontinuation procedures are described in Section 8.5.

Follow-up of AEs and SAEs leading to study discontinuation is discussed in Section 8.5.

11 EFFICACY ASSESSMENTS

The Schedule of Assessments (Table 1) outlines the efficacy assessments to be performed throughout the study and their timing.

11.1 Subject eDiary

- Subjects will be provided access to an eDiary and completion instructions at the baseline visit (Day 1). Adequate time should be allocated on Day 1 to ensure that the subject understands how to access the eDiary portal to complete the daily eDiary and is willing and able to do so every day throughout the study. **NOTE:** The objectives and endpoints for this study relies on subject reported data collected via the eDiary. It is critical that the Investigator and subject understand that accurate, complete, and contemporaneous eDiary data is required to meet the study primary objective. It is particularly important to ensure that each subject completes the eDiary every day. The eDiary will have reminders for subjects to take the study drug and to complete the eDiary daily. The site will check the portal to be sure the subject is completing the eDiary daily. It is suggested that the sites should call the subject on Day 2 about eDiary completion if it is felt the subject will not remember.

Subjects will be asked to record the following details in their eDiary:

- Number of doses taken in the previous 24 hours
- Oral body temperature at the time of diary completion
- Highest oral temperature obtained in the last 24 hours (if additional temperatures were obtained the previous day that were not recorded in the diary the day before)

Information from the eDiary will be used directly for analysis of the secondary endpoints. The Investigator or designee will be required to monitor the subject's eDiary entries and contact the subject to discuss any omissions or inaccurate entries.

11.2 Hospitalization (Primary Efficacy Endpoint)

Hospitalization is defined as the subject's status changing from ambulatory care to COVID-19 related hospitalization or death due to any cause before Day 28. Presenting to the emergency room is considered hospitalization.

11.3 Resolution of Fever (Secondary Efficacy Endpoint)

Body temperature will be measured orally and recorded daily. Oral temperature will also be collected by study staff at an onsite study visit. Subjects will be given an oral temperature device and instructed in the proper use of the device at the Day 1 visit. Temperatures are to be recorded in the eDiary every day from Day 1 through Day 15.

11.4 Viral Shedding

Subjects will have mid-turbinate nasal samples taken using flocked swabs at onsite study visits according to [Table 1](#). Investigators and study site staff will be trained on proper mid-turbinate nasal sample collection and handling of the swab after the sample has been collected. The proper handling of the swab after the nasal sample has been collected are described in the laboratory manual. The procedure for collecting mid-turbinate swabs is also located in [Appendix 2](#). The same nostril should be used for sampling each time it is done, and the nostril (right or left)

should be recorded on the eCRF. Processing samples should be performed according to the central lab manual instructions.

Swab samples will be tested for COVID-19 virus using RT-PCR. Results will be reported as either yes or no for shedding the virus.

